3. TRIAL ENDPOINTS

3.1 PRIMARY ENDPOINT

The primary endpoint in EPoS I, II and III is CRC incidence. CRC incidence will be compared in the different arms in EPoS I and II, and in EPoS III.

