6. RANDOMIZATION

Randomization and data management will be done centrally for this trial. Eligible individuals will be invited to participate in the study and provide written informed consent prior to randomisation. Randomisation must be performed within 26 weeks (182 days) from baseline colonoscopy. Central randomization into the relevant trial (EPoS I, II or III) will be done using the Frontier Science randomisation system for all subjects, depending on their polyp characteristics. Subjects in EPoS I and II will be assigned to a corresponding treatment arm in a 1:1 ratio, depending on the additional stratification factors of site, age and sex.

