11. STATISTICAL ANALYSIS PLAN

Participants are followed for the primary endpoint (incidence of CRC), until death/incidence of CRC or end of follow-up, whichever happens first. All randomised participants are followed up through national or regional registries, regardless of whether they continue in the study or not. The primary analytic approach of the trial will follow the intention-to-treat (ITT) principle. We will compare the ~~average rate~~

~~of differences for~~ each endpoint between the intervention groups by calculating risk differences and log-rank test ~~fitting a Cox proportional hazards model~~. The limit for the statistical significance will be established in 0.05 and 95% confidence intervals will be calculated. If the distribution of any baseline characteristics is found to be imbalanced between the arms, we will conduct a sensitivity analysis in which those characteristics will be included as covariates in the model.

We will also do analyses to estimate the causal effect that would have been observed if all individuals in the intervention arms had been compliant. We will refer to these analyses as “adherence-adjusted” analyses. We will use two different analytic approaches to obtain “adherence-adjusted” estimates: instrumental variables methods and inverse probability weighting. For comparability, we will translate the estimates from both approaches into a common metric: adjusted (CRC-free) survival curves. To implement instrumental variables methods (with the indicator for treatment arm as the instrument), we will use g-estimation of nested structural models. To implement inverse probability weighted estimation, we will estimate the weights and the parameters of a marginal structural Cox model. The estimation of inverse probability weights in one intervention arm requires the measurement of variables that jointly predict compliance with the baseline intervention and the endpoint. These variables include age, sex, baseline findings, physical activity, family history of colorectal cancer, smoking status, use of aspirin, NSAIDs, and hormone replacement therapy (9).

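### The only covariate adjustment of the ITT comparison is triggered by observed imbalance and placed in a model the protocol no longer contains; no use of the randomisation factors is stated

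*Protocol*

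**What the plan says.** Section 6 (Randomization) has participants in EPoS I and II "assigned to a corresponding treatment arm in a 1:1 ratio", with the allocation made "depending on the additional stratification factors of site, age and sex". Section 3.1 fixes the endpoint: "The primary endpoint in EPoS I, II and III is CRC incidence".

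Section 11 (Statistical Analysis Plan) then compares "each endpoint between the intervention groups by calculating risk differences and log-rank test". The words "fitting a Cox proportional hazards model" stand at the end of that sentence but are struck through. No strata or covariates are named for this comparison.

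The next relevant sentence opens with a condition: "If the distribution of any baseline characteristics is found to be imbalanced between the arms". What follows when the condition is met is stated as "we will conduct a sensitivity analysis in which those characteristics will be included as covariates in the model". It gives no list of characteristics, no threshold and no time at which balance is judged.

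The models still named in the section belong to the adherence-adjusted analyses, for which "we will estimate the weights and the parameters of a marginal structural Cox model" and a nested structural model is fitted by g-estimation. Section 11.1 judges non-inferiority on the upper 95% confidence limit of the absolute difference in 10-year cumulative incidence, against 0.5% in EPoS I and 0.7% in EPoS II.

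**The concern.** Three things do not fit together.

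- **The sensitivity analysis refers to a model that has gone.** With the Cox model deleted, the ITT comparison has no regression model to hold covariates. Restoring it would not be enough, because a hazard ratio cannot be read against an absolute margin without conversion.
- **The trigger selects on the wrong property.** Under central randomisation, baseline differences arise by chance. A flagged variable may be irrelevant to colorectal cancer, while a strongly prognostic but balanced variable would never be adjusted for.
- **The design factors are not mentioned in the analysis.** Site, age and sex balance the arms. An analysis that ignores them gives slightly wide intervals.

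At stake is the usefulness of the robustness check. EPoS I expects about 68 events per arm (6,783 × 0.01). If the confidence limit falls near the margin, readers will look to an adjusted analysis, and one with an open covariate set and no stated model would give little support.

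**Working it through.** **1. The text side by side.** The ITT methods in force are a risk difference and a log-rank test. Neither, as named, is a covariate model. The remaining models answer a different question (the effect under full adherence). So the phrase about covariates in the model has nothing to refer to.

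**2. The plan's own sample sizes.** With no strata and a true difference of zero, n per arm = (z₁₋α + z_power)² × 2p(1−p) / margin², with one-sided α = 0.05. The inputs come from section 11 (Sample Size Calculation).

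- EPoS I: 2 × 0.01 × 0.99 / 0.005² = 792. Times 8.564 (90% power) gives 6,783; times 6.183 (80%) gives 4,897.
- EPoS II: 2 × 0.02 × 0.98 / 0.007² = 800. Times 8.564 gives 6,852; times 6.183 gives 4,947.

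All four entries in Table 2 reproduce exactly after rounding up, so nothing below alters a stated figure.

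**3. How often chance alone would trigger adjustment.** Section 3.3 names nine variables. Section 11 adds six: physical activity, family history, smoking, aspirin, NSAIDs and hormone therapy. That makes 15. Age and sex are balanced by stratification, which leaves 13 for EPoS II. In EPoS I, eligibility (section 4.3.1) also fixes growth pattern and dysplasia grade, which leaves 11. The check level and independence are assumptions; the Protocol states neither. The chance of at least one flag is 1 − (1 − level)^k.

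| Trial | k | 5% check | 1% check |
|---|---|---|---|
| EPoS I | 11 | 1 − 0.95¹¹ = 43% | 1 − 0.99¹¹ = 10% |
| EPoS II | 13 | 1 − 0.95¹³ = 49% | 1 − 0.99¹³ = 12% |

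**4. The cost of ignoring the randomisation factors.** Let CV be the coefficient of variation of 10-year risk across site, age and sex strata. The Protocol does not give it; 0.3 to 1.5 is assumed. With balance within strata, the true variance per person is p(1−p) − (CV × p)². Write SE₀ for the standard error that ignores strata and SE₁ for the one that uses them. Then:

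- actual one-sided α of the unstratified analysis = 1 − Φ(1.645 × SE₀/SE₁)
- its power = Φ((margin − 1.645 × SE₀)/SE₁)
- power of the stratified analysis = Φ(margin/SE₁ − 1.645)

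Example, EPoS II with CV 1.5: 0.0196 − (1.5 × 0.02)² = 0.0187, a 4.6% fall in variance. SE₀ = 0.00239 and SE₁ = 0.00234.

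| Trial | CV | Variance reduction | Actual α, unstratified | Power, unstratified | Power, stratified |
|---|---|---|---|---|---|
| EPoS I | 0.3 | 0.1% | 0.0499 | 90.0% | 90.0% |
| EPoS I | 1.0 | 1.0% | 0.0491 | 90.1% | 90.3% |
| EPoS I | 1.5 | 2.3% | 0.0481 | 90.3% | 90.6% |
| EPoS II | 0.3 | 0.2% | 0.0498 | 90.0% | 90.1% |
| EPoS II | 1.0 | 2.0% | 0.0483 | 90.2% | 90.5% |
| EPoS II | 1.5 | 4.6% | 0.0461 | 90.5% | 91.2% |

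The largest power gap is 0.6 points. At one-sided 0.025, which an upper 95% limit implies, the largest gap is 1.1 points (83.9% against 85.0%, EPoS II, CV 1.5).

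**The case against.** The strongest reply is that little depends on this sentence. It governs a sensitivity analysis, so the primary estimate, the decision rule and the sample size are untouched. That stands, and it limits the weight of the point.

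Four stronger readings are tempting, and the Protocol does not support them.

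- *A reader might infer that the primary comparison is definitely unstratified.* The text is silent. A separate analysis plan could name a stratified test, and sizing on two independent proportions is a common simplification. All that can be said is that the Protocol states no use of the factors.
- *A reader might infer that the estimate will be chosen once outcomes are known.* Baseline data are fixed at entry and could be checked long before year 10. The timing is left open; the text does not tie the check to seeing results.
- *A reader might infer that covariates enter nowhere else.* Age, sex, baseline findings and other variables enter the inverse probability weights unconditionally. The point concerns the ITT comparison alone.
- *A reader might count all 15 variables and report a 54% trigger rate (1 − 0.95¹⁵).* That count includes variables balanced by stratification or, in EPoS I, fixed by eligibility. Some of the others, such as polyp size and growth pattern, are unlikely to be independent.

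It can also be said that risk differences may be estimated by regression and log-rank tests may be stratified. True, but the Protocol names neither approach, and choosing one is exactly the decision it leaves unmade.

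**Conclusion.** The point holds as a specification fault of modest size. The firm part rests on stated text: the only adjustment of the ITT comparison depends on observed imbalance, with no threshold or list, and refers to a model that has been struck out. It cannot be run as written.

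The trigger rates of 43% and 49% depend on an assumed 5% check and on independence, and fall to about 10% and 12% at 1%. They show that the trigger is loose; they do not predict what will happen.

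The stratification part is secondary and rests partly on silence. If the factors are ignored, the test is slightly conservative (one-sided α between 0.046 and 0.050 at nominal 0.05) and loses about 1 point of power at most over the assumed CV range. It does not raise the risk of a false claim of non-inferiority, and the validity of the trials is not threatened.

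**What to change.** Replace the imbalance-triggered sentence with one fixed sensitivity analysis for each trial. It should adjust for age, sex and baseline polyp characteristics whatever the observed balance, and be reported as a standardised 10-year risk difference with its 95% interval, so that it can be read against 0.5% or 0.7%. List the polyp characteristics separately for each trial, since growth pattern and dysplasia grade do not vary in EPoS I. Name the working model used for standardisation.

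State also that the primary risk difference and log-rank test account for age and sex, and for site pooled to country where sites are sparse. The risk difference should come from a cumulative-incidence estimator that handles censoring and death. A plain Mantel-Haenszel difference of proportions would treat follow-up as complete.

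The cost is wording, with no new data. Small sites must be pooled and age bands fixed in advance, because events are few for fine strata: about 136 in EPoS I (2 × 6,783 × 0.01) and 274 in EPoS II (2 × 6,852 × 0.02) across both arms. The non-inferiority decision rule and the sample sizes do not change.

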4.3 SPECIFIC DESIGNS AND SETTINGS

4.3.1. EPoS I

Eligible individuals are persons with low-risk adenomas removed at baseline colonoscopy (1-2 tubular adenomas size <10mm with low-grade dysplasia) and no serrated polyps with dysplasia, with diameter 10 mm or larger at any location or with diameter 5 mm or larger proximal to the splenic flexure.

Individuals will be **randomized** into one of two intervention groups:

Group 1: Surveillance colonoscopy at 5 and 10 years after baseline colonoscopy.

Group 2: Surveillance colonoscopy at 10 years after baseline colonoscopy.

The primary and secondary endpoints will be analyzed directly after the 10 year surveillance colonoscopy, (figure 1).

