4.3.2 EPoS II

Eligible individuals are persons with high-risk adenomas removed at baseline colonoscopy (three to ten adenomas; or one or more adenoma w/size \geq 10mm, or one or more adenoma with high-grade dysplasia or villous growth pattern).

Individuals will be **randomized** into one of two intervention groups:

Group 1: Surveillance colonoscopy 3 and 5 years after baseline colonoscopy

Group 2: Surveillance colonoscopy 5 years after baseline colonoscopy

Feb 11th 2017

Individuals in both group 1 and group 2 will be subjected to a final colonoscopy surveillance after 10 years (figure 1).

The primary and secondary endpoints will be analysed directly after the 10 year surveillance colonoscopy, (figure 1). A secondary analysis will be performed after the 5 year colonoscopy.

For centers with current guidelines for 1 year surveillance for multiple or large (>20mm) adenomas; they may exclude those patients.

In both EPoS I and EPoS II, surveillance intervals after the first surveillance colonoscopy take into account findings at the first surveillance colonoscopy. Surveillance intervals after first surveillance colonoscopy are shown in **Figure 2A (EPoS I) and-B (EPoS II)**.

Figure 2. Surveillance intervals after first follow-up colonoscopy in EPoS I and II

Figure 2A: EPoS I

[figure not shown]
[figure not shown]

Figure 2B; EPoS II

LRA: Low risk adenoma; HRA: High-risk adenoma

Figure 2C: Polyp characteristics and eligibility in EPoS. SP: Serrated polyp, TSA: Traditional Serrated Adenoma.

Serrated polyp	≥10mm SP and/or SSA with dysplasia and/or TSA	≥5mm SP in the proximal colon	<10mm SP with no dysplasia in the distal colon	<5mm SP with no dysplasia in the proximal colon	None
No adenoma	EPoS III	EPoS III	No inclusion	No inclusion	No inclusion
1-2 tubular adenoma <10mm with low-grade dysplasia	EPoS III	EPoS III	EPoS I	EPoS I	EPoS I
>2 adenoma	EPoS II	EPoS II	EPoS II	EPoS II	EPoS II
Villous histology	EPoS II	EPoS II	EPoS II	EPoS II	EPoS II
High grade dysplasia	EPoS II	EPoS II	EPoS II	EPoS II	EPoS II
Adenoma ≥10mm	EPoS II	EPoS II	EPoS II	EPoS II	EPoS II

4.3.3. EPoS III;

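### The weighted adherence-adjusted survival curves come from a marginal structural Cox model with no stated time-varying arm effect, although the schedules let the arms differ only from year 5 (EPoS I) or year 3 (EPoS II)

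*Protocol*

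**What the plan says.** Protocol section 11 (Statistical analysis plan) compares the arms by intention to treat through "calculating risk differences and log-rank test". The Cox model is struck through at that point and is not part of the current ITT comparison.

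The section then adds adherence-adjusted analyses by two routes. One is g-estimation with the assigned arm as instrument. The other is inverse probability weighting, for which "we will estimate the weights and the parameters of a marginal structural Cox model". The output of both is fixed: "we will translate the estimates from both approaches into a common metric: adjusted (CRC-free) survival curves". The weights are to use "variables that jointly predict compliance with the baseline intervention and the endpoint". The section does not say whether the arm effect in the Cox model is constant or varies with time, whether the weights are stabilised, or when a non-adherent participant stops contributing.

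The schedules are in sections 4.3.1 and 4.3.2:

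- EPoS I: "Group 1: Surveillance colonoscopy at 5 and 10 years after baseline colonoscopy", against "Group 2: Surveillance colonoscopy at 10 years after baseline colonoscopy".
- EPoS II: "Group 1: Surveillance colonoscopy 3 and 5 years after baseline colonoscopy", against "Group 2: Surveillance colonoscopy 5 years after baseline colonoscopy", with a final examination at 10 years in both arms.

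**The concern.** Until the first examination that only one arm receives, participants who follow the protocol are treated identically. Apart from the 6-month window around each examination (section 4.1.2), the hazard ratio under full adherence is therefore 1 up to year 5 in EPoS I and year 3 in EPoS II. Section 11.1 rests on the premise that removing precursor lesions prevents cancer, so harm from the longer interval can appear only later. If there is any effect, proportional hazards fails by design, and this is known before any data exist.

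A Cox model with one arm coefficient spreads the late effect over the whole follow-up. Its two curves must separate from the start and cannot coincide first and diverge later. The single coefficient also depends on how much weighted follow-up remains in the late period. If that thins out, the early years without effect pull the estimate towards no difference.

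At stake are the curves themselves, which are the stated deliverable of this analysis and the scale on which it is to be compared with g-estimation.

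**Working it through.** **The plan's own figure.** Table 2 follows from n = 2p(1−p)(z₀.₉₅ + z₀.₉₀)²/m², with (1.6449 + 1.2816)² = 8.564.

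- EPoS I: 2 × 0.01 × 0.99 × 8.564/0.005² gives 6,783.
- EPoS II: 2 × 0.02 × 0.98 × 8.564/0.007² gives 6,852.

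Both match. The table's P2 is thus the limit of the margin, and the sample size assumes equal true risks. The check below sets the true difference at that limit.

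**Inputs.** Risks come from Table 2: 1.0% and 1.5% (EPoS I), 2.0% and 2.7% (EPoS II). The protocol gives no timing of cancers, adherence or death rate, so these are assumptions:

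- Half of the shorter-arm cancers occur by year 5 in EPoS I, and 30% by year 3 in EPoS II.
- Adherence at the separating examination is 70% to 90%.
- No cancers are brought forward by the examination.

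Let E and L be the risk (in percentage points) before and after the separating examination, with subscript 0 for the shorter-interval arm and 1 for the longer. EPoS I has E₀ = E₁ = 0.5, L₀ = 0.5, L₁ = 1.0. EPoS II has E₀ = E₁ = 0.6, L₀ = 1.4, L₁ = 2.1. Let c₀ and c₁ be the weighted fraction still at risk after that examination. With full adherence, or unstabilised weights that restore the risk sets, c = 1. With censoring at the examination and stabilised weights, c is the adherence.

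**Formulas (rare events).** The constant hazard ratio θ solves

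E₁ + c₁L₁ = (E₀+E₁)·θ/(1+θ) + (c₀L₀+c₁L₁)·c₁θ/(c₀+c₁θ).

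The Breslow baseline increments are a = (E₀+E₁)/(1+θ) and b = (c₀L₀+c₁L₁)/(c₀+c₁θ). The model's risk difference is (θ−1)a at the separating examination and (θ−1)(a+b) at 10 years. When c₀ = c₁ = c, θ = (E₁+cL₁)/(E₀+cL₀).

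**Two EPoS I cases in full.**

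- Full adherence: θ = 1.5/1.0 = 1.5, a = 1.0/2.5 = 0.40, b = 1.5/2.5 = 0.60. The year-5 gap is 0.5 × 0.40 = 0.20 and the 10-year difference is 0.5 × 1.00 = 0.50.
- 70% in both arms: θ = (0.5+0.7)/(0.5+0.35) = 1.412, a = 1.0/2.412 = 0.415, b = 1.05/(0.7 × 2.412) = 0.622. The year-5 gap is 0.171 and the 10-year difference is 0.412 × 1.037 = 0.427.

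**All cases** (adherence shorter/longer arm; true gap at the separating examination is 0)

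| Trial | Adherence | θ | Gap at separating exam | 10-year difference | True 10-year difference |
|---|---|---|---|---|---|
| EPoS I | full | 1.500 | 0.200 | 0.500 | 0.500 |
| EPoS I | 90/90 | 1.474 | 0.192 | 0.479 | 0.500 |
| EPoS I | 80/90 | 1.456 | 0.186 | 0.467 | 0.500 |
| EPoS I | 70/90 | 1.435 | 0.179 | 0.452 | 0.500 |
| EPoS I | 70/70 | 1.412 | 0.171 | 0.427 | 0.500 |
| EPoS II | full | 1.350 | 0.179 | 0.700 | 0.700 |
| EPoS II | 90/90 | 1.339 | 0.174 | 0.681 | 0.700 |
| EPoS II | 80/90 | 1.331 | 0.170 | 0.669 | 0.700 |
| EPoS II | 70/90 | 1.322 | 0.166 | 0.655 | 0.700 |
| EPoS II | 70/70 | 1.310 | 0.161 | 0.631 | 0.700 |

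Without the rare-event shortcut, the EPoS I 10-year values for full, 80/90, 70/90 and 70/70 are 0.499, 0.465, 0.451 and 0.426.

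**Censoring by death.** Take 1.5% a year in both arms. The mean fraction alive is about exp(−0.015 × 2.5) = 0.963 early and exp(−0.015 × 7.5) = 0.894 late. Then θ = (0.963 × 0.5 + 0.894 × 1.0)/(0.963 × 0.5 + 0.894 × 0.5) = 1.481, and the EPoS I 10-year difference is 0.481 × (1.0 + 1.5)/2.481 = 0.485. A separate calculation in which some cancers are found at the examinations gives 0.474 at 1.5% a year and 0.450 at 3%. Its EPoS II counterpart gives 0.679 at 1.5% a year.

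**The alternative.** A weighted Kaplan-Meier curve divides each arm's late events by its own risk set. The gap is E₁ − E₀ = 0 at the separating examination, and the late part is c₁L₁/c₁ − c₀L₀/c₀ = L₁ − L₀. The true difference returns at both times, whatever c is.

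**The case against.** The main counter-argument is that the protocol does not state a constant hazard ratio. A marginal structural Cox model can carry arm-by-time terms, and a SAP not shown here may specify them. This stands. A reader might infer that the planned curves are wrong outright; the text supports only that they are misshapen in the usual constant-ratio form, which it leaves open.

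Second, non-proportionality alone does not bias the 10-year result, which is the main analysis time. With no censoring, or with risk sets in a fixed ratio throughout, the 10-year difference is 0.499. The wording on compliance with the baseline intervention does not settle when non-adherers are censored, and stabilisation is not mentioned. This also stands for the adherence route. Censoring by death needs no such choice: section 11 ends follow-up at death, and participants are 40 to 74 at entry.

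Third, the 10-year bias is modest. For EPoS I the weighted Kaplan-Meier standard error, √[(E₀ + L₀/c₀ + E₁ + L₁/c₁)/n] with risks as proportions, is about 0.20 to 0.22 points. A bias of 0.03 to 0.07 is roughly 0.15 to 0.35 of that. With equal true risks and no cancers brought forward, there is no bias.

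Fourth, it is tempting to read this as a raised chance of a false non-inferiority claim. The documents do not support that. Section 11.1 applies the 0.5% and 0.7% margins to the 10-year absolute difference, ITT is the primary approach, and no margin test is attached to the adherence-adjusted curves. G-estimation is also planned as a second adherence-adjusted method.

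**Conclusion.** The point holds in a limited form. By the protocol's own schedules, hazards under full adherence are non-proportional if the longer interval has any effect, and section 11 names a Cox model without providing for this.

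Under a constant hazard ratio, the EPoS I curves show about 0.17 to 0.20 points of difference at year 5 where there is none. This early error overstates harm. It should not be scaled against the 0.5% margin, which is defined at ten years. The 10-year difference is essentially correct without censoring. With death censoring, or with stabilised weights and censoring at the separating examination, it is understated: about 0.43 to 0.48 instead of 0.50 in EPoS I, and 0.63 to 0.68 instead of 0.70 in EPoS II. These sizes depend on the assumed timing of cancers, adherence and death rates.

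A reader might also infer that the hazards cross at the examinations. That requires cancers detected at the extra examination, for which the protocol gives no rate, so crossing is possible but not established.

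The ITT non-inferiority decision does not change. The weakness lies in one supplementary analysis, but it is foreseeable and cheap to remove.

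**What to change.** In section 11, replace the marginal structural Cox model with inverse-probability-weighted Kaplan-Meier (or weighted cumulative incidence) curves for each arm. Alternatively, keep a model but require arm-by-time terms with a break at the separating examination: year 5 in EPoS I and year 3 in EPoS II. In either case, report the adherence-adjusted 10-year risk difference with a bootstrap 95% confidence interval, so that it is on the same scale as the ITT risk difference.

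The cost is about one sentence in the protocol, a little more programming, and a slightly wider interval than a proportional hazards model would give. No new data or participants are needed, and the sample size does not change.
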